# 4.2.5. Multiple Comparisons/Multiplicity

Multiplicity is not of concern for this study with a single primary efficacy endpoint.

## 4.2.6. Subpopulations

The following subgroups will be considered:

- Age at randomisation: 0 to <2 year/ ≥2 year to <6 years/ ≥6 years to <12 years/ ≥12 years to ≤18 years
- Gender: Male/Female
- Region: Europe/Rest of the World/United States

Europe and Rest of the World maybe pooled under Non-US if Rest of the World represents a low number of subjects (e.g. less than 5% of the overall Safety Population).

In case of imbalance between treatment groups regarding baseline characteristics, other subgroup analyses may be performed.

#### 4.2.7. Withdrawals, Dropouts, Loss to Follow-up

Subjects who withdrew from the study were not to be replaced.

#### 4.2.8. Missing, Unused, and Spurious Data

All data recorded on the CRF will be included in data listings that will accompany the clinical study report.

In general there will be no imputation of missing data. There are a few exceptions where data imputation will be implemented see paragraph below.

4.2.8.1. Primary endpoint and secondary efficacy endpoints related to change in serum phosphorus levels from baseline to the end of Stage 1

To compute the change from baseline in serum phosphorus at end of stage 1, the laboratory values post-baseline and at baseline should be from the same source (i.e. either both central or both local). In addition, the following steps will be followed regarding the value to be considered at end of stage 1 for serum phosphorus:

- Step 1: Take central laboratory value at Visit 11 (visit n) if available.
- Step 2: If central laboratory value at Visit 11 is not available, then the central laboratory value at the previous visit, if available, is to be used. The previous visit to be called visit (n-1) will be the latest visit between Visit 16 (if subject early withdrew during stage 1) and Visit 10.
- Step 3: If central laboratory value at visit (n-1), as defined above, is not available, if local laboratory values at Visit (n-1) and at baseline are both available for the subject, then local laboratory value at Visit (n-1) is to be used.
- Step 4: If local laboratory value at Visit (n-1) is not available or if local laboratory value at baseline is not available, then the central laboratory value at visit (n-2) will be considered.
- Step 5: Repeat step 3 considering Visit (n-2)
- Step 6: Repeat step 3 and 4 considering visit (n-3),
  - o until visit 1 for PB naive subjects
  - o until visit 2 for subjects on PB

Note: "Visit 11", "Visit 16" and more generally "Visit x" will refer to the derived analysis visits (applying windowing as defined in section 4.2.9).

4.2.8.2. Secondary efficacy endpoints related to change in serum phosphorus levels from baseline to the end of Stage 2

To compute the change from baseline in serum phosphorus at end of stage 2, the laboratory values post-baseline and at baseline should be from the same source (i.e. either both central or both local). In addition, the following steps will be followed regarding the value to be considered at end of stage 2 for serum phosphorus. Of note Visit 16 will be taken into account only if subject did not early withdraw during stage 1:

- Step 1: Take central laboratory value at Visit 16 (visit n) if available.
- Step 2: If central laboratory value at Visit 16 is not available then the central laboratory value at the previous visit, Visit (n-1) (i.e. visit 15), is to be used, if available.
- Step 3: If central laboratory value at Visit (n-1) is not available, if local laboratory values at Visit (n-1) and at baseline are both available for the subject, then local laboratory value at Visit (n-1) is to be used.

- Step 4: if local laboratory value at Visit (n-1) or local baseline are not available, central laboratory value at Visit (n-2) is to be used.
- Step 5: Repeat step 3 considering Visit (n-2)
- Step 6: Repeat step 4 and 5 for Visit (n-3), until Visit 12

Note: "Visit 16", "Visit 15" and more generally "Visit x" will refer to the derived analysis visits (applying windowing as defined in section 4.2.9).

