## 4.7.1. Primary Efficacy Endpoint

The primary efficacy endpoint is the change in serum phosphorus levels from baseline to the end of Stage 1 (i.e. considering the last available value in stage 1) in PA21 group. It is based on central laboratory data; in case of missing data regarding central laboratory data, local laboratory measurements are used (please refer to Section 4.2.8.1 for the imputation to be applied).

The change from baseline in the PA21 group will be analysed using a linear mixed model with treatment, baseline serum phosphorus, age (in categories) at randomisation, region and gender as fixed effects. Summary statistics with the estimate of the adjusted mean change from baseline and its 95%CI as well as the corresponding p-value from the t-test will also be provided.

The SAS code used for the linear mixed model will be as below:

```
proc mixed data=input method=type3;
    class treatment age region gender;
    model chg_end_stage1=treatment age region gender baseline / ddfm=KENWARDROGER solution;
    lsmeans treatment / CL alpha=0.05;
    where treatment='PA21';
    ods output lsmeans=lsm1;
```

run;

The primary efficacy analysis will be repeated on the FAS by the following subgroups:

- Formulation (tablets only/sachets only/both)
- Serum phosphorus at baseline according to the age related normal range (above, within + below; see Table 5)
- Age group at randomisation (0-<2, 2-<6, 6-<12, 12-<=18) \* Serum phosphorus at baseline according to the age related normal range (above, within + below; see Table 5). In case of no subject in an age group, this category will not be displayed.

Sensitivity analyses will include a repeat of the primary analysis on the FAS population based on observed data from the central laboratory only (with no imputation by local laboratory data).

Homogeneity of the results of the primary endpoint will be investigated on the FAS population by displaying summary statistics of change from baseline with the estimate of the adjusted mean change from baseline and its 95%CI for the following subgroups using the same linear mixed model as above:

- By age group at randomisation
- By gender
- By region

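### The end-of-stage derivation steps never admit a local laboratory value at Visit 11 (Stage 1) or Visit 16 (Stage 2), so where one exists with a local baseline an older value is used instead

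*SAP*

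**What the plan says.** Section 4.2.8.1 sets the order for the end of Stage 1. It opens with "Step 1: Take central laboratory value at Visit 11 (visit n) if available". Step 2 reads "If central laboratory value at Visit 11 is not available, then the central laboratory value at the previous visit", and visit (n-1) "will be the latest visit between Visit 16 (if subject early withdrew during stage 1) and Visit 10". Step 3 is the first to admit a local value, at visit (n-1), and only "if local laboratory values at Visit (n-1) and at baseline are both available for the subject". Later steps alternate central and local at each earlier visit. Baseline and post-baseline values must come from the same laboratory source.

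Section 4.2.8.2 follows the same order for the end of Stage 2: central Visit 16, then "If central laboratory value at Visit 16 is not available then the central laboratory value at the previous visit" (Visit 15), then local Visit 15, and so on back to Visit 12.

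Section 4.7.1 defines the primary endpoint as "considering the last available value in stage 1" and adds that "in case of missing data regarding central laboratory data, local laboratory measurements are used", referring to 4.2.8.1 for details. Sections 2.5.1.1, 2.5.1.2 and 4.7.2 state the same general local fallback.

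**The concern.** At every visit before the last, the steps try the central value, then the local value, and only then go back a visit. At visit n itself the local step is absent. If the central Visit 11 sample is lost or unusable and a local result falls in the Visit 11 window, the steps pass over that result even when a local baseline is there to pair with it. The value then used is not the last available one in Stage 1. The same happens at Visit 16.

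At stake is the derivation of the only formally tested endpoint, and of the corresponding Stage 2 secondary endpoint. One programmer working from the definition in 4.7.1 and another from the steps in 4.2.8.1 could derive different values for the same child.

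**Working it through.** **The SAP's own figure.** The point disputes no number. For context, section 4.1 claims more than 90% power for PA21 with 100 randomised, 30% drop-out, mean change 1.2 mg/dL and SD 2.0. With n = 100 × (1 − 0.30) = 70, the noncentrality is 1.2 / (2.0/√70) = 5.02, and a two-sided 0.05 one-sample t-test has 99.9% power. The claim is reproduced. The fallback order is not an input to it.

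**Order of the steps, side by side.**

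| Visit | Stage 1 | Stage 2 |
|---|---|---|
| n | Visit 11: central only | Visit 16: central only |
| n-1 | Visit 10 (Visit 16 for Stage 1 withdrawals): central, then local | Visit 15: central, then local |
| n-2 and earlier | central, then local | central, then local |

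Local (n-1) in Step 3 ranks above central (n-2) in Step 4, so the steps prefer a recent local value to an older central one everywhere except at visit n.

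**Walking example data through the steps.** Each child has a central baseline and no central value at visit n. The only central post-baseline value is at Visit 8 (Stage 1) or Visit 13 (Stage 2).

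| Case | Local values available | As written | With a local step at visit n |
|---|---|---|---|
| Stage 1, local baseline | Visits 11, 10, 9 | local Visit 10 | local Visit 11 |
| Stage 1, no local baseline | Visits 11, 10, 9 | central Visit 8 | central Visit 8 |
| Stage 1, local baseline, no local Visit 11 | Visits 10, 9 | local Visit 10 | local Visit 10 |
| Stage 1 ended at Visit 9, local baseline | Visit 9 | local Visit 9 | unchanged |
| Stage 1 withdrawal, local baseline | Visits 16, 10 | local Visit 16 | unchanged |
| Stage 2, local baseline | Visits 16, 15, 14 | local Visit 15 | local Visit 16 |
| Stage 2, no local baseline | Visits 16, 15, 14 | central Visit 13 | central Visit 13 |

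Only the first and sixth cases change.

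**How much older the substituted value is** (windows from section 4.2.9).

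- Stage 1: Visit 10 is Day 57 ± 3 (54 to 60) and Visit 11 is Day 71 ± 7 (64 to 78). Nominal gap 71 − 57 = 14 days; smallest 64 − 60 = 4; largest 78 − 54 = 24.
- Stage 1, Visit 10 unusable too: 71 − 43 = 28 days nominally (Visit 9), or 71 − 29 = 42 days (Visit 8) if Visit 9 is also unusable.
- Stage 2: Visit 15 is Day 127 ± 7 (120 to 134) and Visit 16 is Day 169 ± 7 (162 to 176). Nominal gap 169 − 127 = 42 days; smallest 162 − 134 = 28; largest 176 − 120 = 56.

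**Can the pattern arise?** Table 3 requires a central sample at Visits 1, 5, 8, 11, 13 and 16 and marks the local option only at Visits 2–4, 6, 7, 9, 10, 12, 14 and 15. A local value at visit n must therefore be off-schedule or re-windowed. Analysis visits are assigned by day, so an unscheduled local sample, or a local Visit 10 sample taken on Day 64 or later, becomes Visit 11. Section 4.2.9 expects unscheduled values. A local baseline would most likely come from washout Visits 2–4, since section 4.2.1 takes the latest pre-dose measurement as baseline.

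**The case against.** The strongest defence is that the schedule makes the gap nearly empty. No local sample is planned at Visit 11 or 16, and none at baseline Visit 5. Children who need no washout skip Visits 2–4, so the schedule gives them no local baseline, and for them the missing step changes nothing. Children who end Stage 1 at Visit 8, 9 or 10 can have the local value of that visit used. So can Stage 1 withdrawals, for whom Visit 16 is visit (n-1). All of this stands and limits the reach of the point.

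It does not explain the omission. Visits 8 and 13 are also central-required, yet the steps admit local values there. Nor does a deliberate preference for the central laboratory, which would not place local (n-1) above central (n-2).

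A second defence is that the fallback sentences in 2.5.1 and 4.7 are general and refer to 4.2.8 for the detail. That is fair: they do not say the substitution is made visit by visit, so the conflict with them is one of intent. The conflict with the last-available wording in 4.7.1 is direct, though the SAP has no matching phrase for Stage 2.

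A reader might infer three stronger things that the SAP does not support:

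- That every child with a missing central end-of-stage sample loses a usable result. The SAP does not show that such local results exist.
- That the substituted value is always at least 14 days too early. Between adjacent windows the gap can be as short as 4 days.
- That an earlier value understates the effect. Section 2.1 allows doses to go up or down during titration, and no figure supports a direction.

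**Conclusion.** The point holds in conditional form. When the central value at Visit 11 or Visit 16 is missing, and both a local value in that window and a local baseline exist, the steps discard the local value and use an older one. This contradicts the primary endpoint definition in 4.7.1 and the steps' own ordering.

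For an affected child the replacement is nominally 14 days older in Stage 1 and 42 days older in Stage 2, if Visit 10 or Visit 15 is usable, and older still if not. The number of affected children cannot be derived from the SAP. It is probably small, because three things must coincide: a missing central value at visit n, a local sample not foreseen by Table 3, and a local baseline. The stated power is unaffected and no direction of bias can be claimed. This is a small error in a derivation rule, worth correcting because it governs the primary endpoint.

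**What to change.** In both 4.2.8.1 and 4.2.8.2, insert between Steps 1 and 2: *If the central value at Visit n is missing, and a local value at Visit n and a local baseline value are both present, use the local value at Visit n.* Then continue with visit (n-1) as now. The same-source requirement is kept, and no child outside the pattern above gets a different value.

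The cost is one sentence in each of two sections and one extra line of derivation code, with no new data. Before database lock, counting the children whose value would change, without reference to treatment group, would supply the figure that the SAP cannot.

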# 2.5. Efficacy, Pharmacokinetic, and Safety Variables

## 2.5.1. Efficacy Variables

## 2.5.1.1. Primary Efficacy Endpoint

The primary efficacy endpoint is the change in serum phosphorus levels from baseline to the end of Stage 1 in PA21 group. It is based on central laboratory data; in case of missing data, the change from baseline will be computed using pre- and post-treatment values from the local laboratory (see Section 4.2.8).

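### Step 6 of the Stage 1 look-up is misindexed: read literally it does not assign the central Visit 8 phosphorus value, and its stopping point lets baseline serve as end of Stage 1

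*SAP*

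**What the plan says.** Section 4.2.8.1 requires baseline and post-baseline values to come from the same laboratory source and sets out an ordered search for the end of Stage 1 value:

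- Step 1: "Take central laboratory value at Visit 11 (visit n) if available".
- Step 2: central value at visit (n−1), which "will be the latest visit between Visit 16 (if subject early withdrew during stage 1) and Visit 10".
- Step 3: the local value at (n−1), under a condition that begins "If central laboratory value at visit (n-1), as defined above, is not available, if local laboratory values at Visit (n-1) and at baseline"; each of those two local values must exist.
- Step 4: if that local pair is incomplete, "then the central laboratory value at visit (n-2) will be considered".
- The fifth step adds the local look-up one visit further back: "Repeat step 3 considering Visit (n-2").
- The sixth and last step is worded "Repeat step 3 and 4 considering visit (n-3"), continuing back to Visit 1 for binder-naive subjects and to Visit 2 for subjects on a phosphate binder.

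The Stage 2 search in section 4.2.8.2 has the same steps 3 to 5 but ends differently: "Repeat step 4 and 5 for Visit (n-3), until Visit 12".

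Section 2.5.1.1 says of the primary endpoint: "It is based on central laboratory data; in case of missing data, the change from baseline will be computed using pre- and post-treatment values". Local measurements are the fallback source. Section 4.7.1 defines end of Stage 1 as the final value obtained in that stage. Section 4.2.9 attaches the End of Stage 1 label to Visit 11 or to whichever earlier visit precedes entry to Stage 2.

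**The concern.** The two searches should follow one pattern, and they do not. Steps 4 and 5 both concern visit (n−2): central, then local. Moving that pair back one visit gives central then local at (n−3). Steps 3 and 4 concern two different visits: local at (n−1), then central at (n−2). Moving that pair back leaves a gap at the central value of (n−3).

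For most subjects (n−3) is Visit 8. Subjects may enter Stage 2 from Visit 8 (section 2.1; Table 2, footnote 5), and section 4.2.1 assigns everything after the last titration visit to Stage 2. A Week 4 mover therefore has no Stage 1 data at Visits 9 to 11, and step 6 alone decides that subject's primary endpoint. Under section 2.1 these are subjects who have reached target phosphorus, so the value at risk is an informative one, not a random loss.

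The stopping point raises a second problem. A search for a post-treatment value should not be able to return a pre-treatment one. This is the only endpoint that is formally tested (section 4.2.1).

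**Working it through.** The SAP gives no figure for this point, so the check is a trace of the rule.

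**Inputs.** n = Visit 11. For a subject who did not withdraw in Stage 1, n−1 = Visit 10, n−2 = Visit 9, n−3 = Visit 8 and n−4 = Visit 7. Table 3 requires a central sample at Visits 1, 5, 8, 11, 13 and 16. It allows the local laboratory at Visits 6, 7, 9 and 10, and schedules phosphorus at Visit 7 but not at Visit 6. Visit 5 is baseline.

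**Substitution.** Step 5 shows how a repeat works: the named visit replaces (n−1). Applied to step 6:

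- Step 3 at (n−3): if central Visit 8 is missing, and local Visit 8 and local baseline both exist, take local Visit 8.
- Step 4 at (n−3): if local Visit 8 or local baseline is missing, take central at (n−4), which is Visit 7.

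With C for central and L for local, the literal order is C11, C10, L10, C9, L9, L8 (only if C8 is missing), C7, L7, C6, L6, C5 and so on. C8 is the only central value from Visit 11 back to Visit 1 that is never looked up. Under the Stage 2 pattern the order is C11, C10, L10, C9, L9, C8, L8 and so on.

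**Outcome for a Week 4 mover with central values at Visits 1, 5 and 8:**

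| Other values held | Literal step 6 | Stage 2 pattern |
|---|---|---|
| None | Central Visit 5: change = 0 | Central Visit 8 |
| Local Visit 7, no local baseline | Central Visit 5: change = 0 | Central Visit 8 |
| Local Visit 7 and local baseline | Local Visit 7 | Central Visit 8 |
| Central Visit 7 | Central Visit 7 | Central Visit 8 |
| Local baseline, Visit 7 and Visit 8 | Local Visit 7 | Central Visit 8 |

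In the last row, neither condition is met at Visit 8: step 3 is barred because the central value exists, and step 4 because the local pair exists. The result shown assumes that the search then continues to Visit 7.

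**Stopping point.** This fault does not depend on the step numbers. Take a subject with a central baseline only and local post-baseline values only. The same-source rule excludes every local value. The search then reaches central Visit 5, and the change is baseline minus baseline = 0. Such a subject has a post-baseline assessment and so can be in the FAS. Section 4.2.8.1 also says that visit numbers mean the windowed visits of section 4.2.9, which defines no window for Visits 1 to 4.

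**Size.** The only available illustration uses the mean change of 1.2 mg/dL from section 4.1 and an assumed share f of Week 4 movers, all set to zero change: mean = 1.2 × (1 − f).

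- f = 10%: 1.2 × 0.90 = 1.08 mg/dL
- f = 30%: 1.2 × 0.70 = 0.84 mg/dL
- f = 50%: 1.2 × 0.50 = 0.60 mg/dL

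**The case against.** The strongest reply is that the intent is plain and a sensible programmer would follow it. Step 4 considers the central value at (n−2). If (n−3) replaces (n−2) there, step 6 gives central Visit 8. Sections 4.7.1 and 4.2.9, and Table 3 footnote 5 (a central sample at the final Stage 1 visit where possible), all point the same way. This stands, and it makes the fault a drafting error with recoverable intent. It requires replacing (n−1) in step 3 but (n−2) in step 4, however, and step 5 replaces (n−1).

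A second reply is that the Stage 2 wording fails the same test: putting (n−3) for (n−1) in its step 4 also gives central (n−4). That is not decisive, because steps 4 and 5 share one target visit and move back together. It is a good reason not simply to copy the Stage 2 sentence.

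Three stronger readings are tempting, and the SAP does not support them:

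- A reader might infer that local Visit 8 would displace an available central Visit 8. Step 3's own condition prevents that.
- A reader might infer that the loss affects everyone. For a Stage 1 withdrawer with n−1 = Visit 16 and n−2 taken as Visit 10, Visit 8 is n−4, and the literal rule reaches its central value.
- A reader might take 1.08 to 0.60 mg/dL as the expected dilution. Those figures need every Week 4 mover to have neither a central Visit 7 value nor a usable local pair, and they need the separate stopping clause to return baseline. Zero changes would also pull the estimate towards no effect, not create one.

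**Conclusion.** The point holds in a limited form. As written, step 6 does not assign the required central Visit 8 value for subjects who stayed in Stage 1 and whose search reaches Visit 8, which includes every Week 4 mover. That conflicts with sections 4.7.1 and 4.2.9. The intended order can be inferred, so it does not follow that the analysis will be wrong. What follows is that the derivation of the sole tested endpoint depends on how a programmer reads one line. The stopping clause is a fault on either reading, because it admits baseline or another pre-treatment value as an end of Stage 1 result. The effect on the estimate cannot be sized from the SAP: the share of Week 4 movers and the availability of local pairs are not given, and 1.2(1 − f) mg/dL is an upper bound on dilution under assumed f.

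**What to change.** Replace step 6 of section 4.2.8.1 with explicit wording such as: *For visit (n−3) and each earlier Stage 1 visit in turn, take the central value if available (with central baseline); otherwise take the local value if the local baseline is also available. Stop at the first post-baseline visit (Visit 6). If no value is found, treat the endpoint as missing.* Delete the continuation to Visit 1 or Visit 2.

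The cost is a few lines of SAP text before database lock and a check that the program follows them. Subjects with no usable post-baseline pair would have a missing change instead of a zero, in line with the general no-imputation statement in section 4.2.8, and their number should be reported. If the derivation has already been run, state which order was programmed and how many subjects would change value.

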#### 4.2.8.3. Glomerular Filtration Rate

For subjects on dialysis values of glomerular filtration rate will not be deemed interpretable. Therefore all eGFR values for subjects on dialysis at screening as well as eGFR values after dialysis for subjects requiring dialysis for the first time during the study will not be part of the summary statistics over time of eGFR, they will be listed only.

